11.4 Formal Interim Analysis and Stopping rules

Formal interim analysis for efficacy and futility:

Using an asymmetric two-sided non-binding two-stage group sequential design with 90% power and 2.5% type-1 error, we will apply a lower bound cut-off rule to conclude futility and upper bound cut-off to determine superiority. After a minimum of 81 events, stage 1 will conclude futility if Z<0.41 (nominal p-value > 0.6599), favouring FMT, or superiority if Z>2.75 (H0: Reject, nominal p<0.006) favouring FMT. Applying type 1-error spending using HwangShih-DeCani and Gamma = -4 (one-sided, stage one spent error =0.003). Using this alpha spending approach, at the final analysis, the null hypothesis for efficacy will be rejected if p<0.047.

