11.1 Sample Size

Moreau *et al.* ⁴¹ performed a double-blind trial of the long-term fluoroquinolone antibiotic norfloxacin *versus* placebo in 291 patients with advanced cirrhosis (Child Pugh C) who had not received recent fluoroquinolone therapy. The study was performed at 18 clinical sites in France. Patients were randomly assigned to groups given 400mg norfloxacin (n=144) or placebo (n=147) once daily for 6 months. The primary outcome was 6-month mortality, as estimated by the Kaplan-Meier method. The Kaplan-Meier estimate for 6-month mortality was 14.8% for patients receiving norfloxacin and 19.7% for patients receiving placebo (p=0.21). In competing risk analysis that took liver transplantation into account, the cumulative incidence of death at 6-months was significantly lower in the norfloxacin group than in the placebo group (sub-distribution hazard ratio, 0.59; 95% confidence interval, 0.35-0.99). Norfloxacin significantly decreased the incidence of any and Gram-negative bacterial infections without increasing infections caused by *Clostridioides difficile* or multidrug-resistant bacteria. We have estimated FMT to be at least as effective as norfloxacin to reduce infection (hazard ratio = 0.625). ⁴⁴

We have assumed that 65% of patients in the control group experience an infection resulting in hospitalisation within 2-years and that this is reduced to 48.9% in the FMT arm. In order to detect this hazard ratio of 0.625, with 80% power (alpha = 0.047) we would need to analyse 270 patients (to experience 155 events). In order to account for a 10% loss to follow up, we will inflate to 300 patients (1:1 ratio). Note: 203 events would provide 90% power to detect this

effect, and 261 events would provide 80% power to detect a HR = 0.70. Using a group sequential design, an interim analysis will be carried out after 81 events (alpha = 0.006).

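### Section 11.4 claims 90% power for a design that Section 11.1 sizes for 80% with 155 events, and 90% is out of reach with 300 patients

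*Protocol*

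**What the plan says.** Section 11.1 (Sample Size) assumes that 65% of control patients have an infection leading to hospitalisation within two years and that "this is reduced to 48.9% in the FMT arm". It continues: "In order to detect this hazard ratio of 0.625", "with 80% power (alpha = 0.047) we would need to analyse 270 patients", who are expected "to experience 155 events". A 10% allowance for loss to follow-up brings the total to 300. The section then adds: "Note: 203 events would provide 90% power to detect this" effect. It places an interim analysis after 81 events with alpha 0.006.

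Section 11.4 (Formal Interim Analysis and Stopping rules) describes what is plainly the same trial, with the same 81-event look and the same final level of 0.047, in these words: "Using an asymmetric two-sided non-binding two-stage group sequential design with 90% power and 2.5% type-1 error". It sets futility at Z below 0.41 and superiority at Z above 2.75 (p below 0.006). The spending function is Hwang-Shih-DeCani with gamma -4, and the one-sided stage 1 spend is 0.003. Section 11.4 gives no final event total, and neither section gives an information fraction.

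**The concern.** The two sections give different powers for one trial, and Section 11.1 itself supplies the figure that rules out the higher one: 90% goes with 203 events, not 155. Power is what an ethics committee, a funder or the data monitoring committee uses to judge how a null result should be read. A reader of Section 11.4 alone would put the risk of missing the planned effect at 10%, when it is about 17% to 19%.

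Because Section 11.4 names no final event total, a reader also cannot tell which total the interim bounds belong to. The hazard ratio and the two event rates in Section 11.1 do not quite agree either, and that bears on whether even 80% is reached.

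**Working it through.** **Inputs.** From Section 11.1: HR 0.625; two-sided alpha 0.047 (critical value 1.986); 155 events for 80% power and 203 for 90%; two-year event rates 65% and 48.9%; 270 analysed, 300 randomised, 1:1. From Section 11.4: interim at 81 events, bounds 2.75 and 0.41, Hwang-Shih-DeCani gamma -4, one-sided type I error 0.025.

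**1. Reproducing the protocol's event counts.** Let z be the sum of the alpha and power quantiles: 1.986 + 0.842 for 80%, 1.986 + 1.282 for 90%.
- Freedman: events = [(1 + HR)/(1 - HR)]² × z²
- Schoenfeld: events = 4 z² / (ln HR)²

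| Target | Protocol | Freedman | Schoenfeld |
|---|---|---|---|
| HR 0.625, 80% | 155 | 151 | 145 |
| HR 0.625, 90% | 203 | 201 | 194 |
| HR 0.70, 80% | 261 | 257 | 252 |

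Freedman comes within 3% of all three figures, so Section 11.1 is coherent on its event counts. The expected yield also agrees: the mean event rate is (0.65 + 0.489)/2 = 0.5695, and 270 × 0.5695 = 153.8. The 10% allowance checks too: 270/0.9 = 300.

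**2. Power of the planned trial.** Fixed-sample power is Φ(δ√D - 1.986), where D is the number of events. Under Freedman δ = 0.375/1.625 = 0.2308; under Schoenfeld δ = |ln 0.625|/2 = 0.2350. The two-stage figures integrate the bivariate normal distribution of the two test statistics, with the stated bounds and the interim at 81 events.

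| Design | Freedman | Schoenfeld |
|---|---|---|
| 155 events, fixed sample | 81.2% | 82.6% |
| 155 events, two-stage, futility ignored | 81.4% | 82.8% |
| 155 events, two-stage, futility followed | 80.5% | 81.9% |
| 171 events, fixed sample | 84.9% | 86.1% |
| 203 events, fixed sample | 90.3% | 91.3% |

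The 171 is the ceiling for this trial at the stated rates: 300 × 0.5695 = 170.9, with nobody lost. Follow-up is 24 months per participant (Section 7.8), so waiting longer adds no events.

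**3. The interim efficacy bound.** The error spent at information fraction t is 0.025 × (e^(4t) - 1)/(e^4 - 1).

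| Fraction | Spend (one-sided) | Z | Two-sided p | Final two-sided p |
|---|---|---|---|---|
| 0.500 (81/162) | 0.0030 | 2.750 | 0.0060 | 0.0476 |
| 0.523 (81/155) | 0.0033 | 2.716 | 0.0066 | 0.0474 |
| 0.399 (81/203) | 0.0018 | 2.905 | 0.0037 | 0.0482 |

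The stated 2.75 and 0.006 are the values for 0.50. If the interim bound of 2.75 and the final level of 0.047 are applied at 81 and 155 events, the one-sided type I error is 0.0246, below 0.025.

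**4. Hazard ratio against event rates.** Under proportional hazards HR = ln(1 - 0.489)/ln(1 - 0.65) = ln 0.511/ln 0.35 = 0.64. Conversely, HR 0.625 gives 1 - 0.35^0.625 = 48.1%. With HR 0.64 (0.6395 unrounded) and 155 events:
- Freedman: 0.3605/1.6395 × √155 = 2.74, less 1.986 = 0.75, power 77%.
- Schoenfeld: 0.4470/2 × √155 = 2.78, less 1.986 = 0.80, power 79%.

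**The case against.** The strongest reply is that nothing in the conduct of the trial depends on the 90%. The number randomised, the final significance level and type I error control are unaffected, and Section 11.1 gives the sizing correctly. That is right about conduct. It does not make the statement in Section 11.4 true.

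A reader might go further and infer that the interim bounds are invalid because they belong to another event total. The documents do not support that. Against 155 events the gap is 2.75 versus 2.72. The spend of 0.0033 rounds to the printed 0.003, the stated bound errs on the conservative side, and the final level of 0.047 fits 81/155 slightly better than 81/162. Section 11.4 also speaks of a minimum of 81 events and names its spending function, so the efficacy bound can be recalculated at the actual look. The mismatch is large only against 203 events, which this trial does not plan.

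A reader might also want the final total fixed at 155 or the look moved to 78 events. That would be guessing at the sponsor's design. If the lower spending function had gamma -2, which the protocol does not state, the group sequential inflation at 80% power would be about 1.042, and 155 × 1.042 = 161.5, close to 162, half of which is 81. The 81 may therefore come from inflating 155 for the interim look. For the same reason no replacement futility value can be offered: the bound depends on a lower spending function that the protocol does not give.

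**Conclusion.** The point holds for the power statement. At HR 0.625 and alpha 0.047 the 155-event design has about 81% to 83% power, or 80% to 82% if the futility bound is followed. That is 7 to 10 percentage points below what Section 11.4 states. The range comes from the choice between Freedman and Schoenfeld. The ceiling of about 171 events rests on the protocol's own event rates and complete two-year follow-up of 300 patients; it gives 85% to 86%, so 90% is not attainable with this design. It does not follow that the trial misses its own 80% target: at the planned hazard ratio it meets it.

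Two secondary points stand, both small. The efficacy bound corresponds to 81 of 162 events, a total that appears nowhere, with no inflation of the type I error. The event rates imply HR 0.64 rather than 0.625; if the rates are the true assumption, power at 155 events is about 77% to 79%, slightly below the 80% claimed.

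**What to change.** 1. In Section 11.4, replace 90% power with 80% power, and state one final event total that is the same in Sections 11.1 and 11.4.
2. State the planned information fraction at the interim, and confirm that the efficacy bound will be recalculated from the named spending function at the actual number of events. The sponsor should also state the lower spending function behind the futility bound.
3. In Section 11.1, reconcile the hazard ratio with the event rates. Keeping 0.625 means changing 48.9% to 48.1%. The expected yield then becomes 270 × (0.65 + 0.481)/2 = 152.7 events, a little further below 155. Keeping 48.9% means stating HR 0.64 and power of about 77% to 79%.

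Item 1 is a wording change that needs no more patients; its only cost is a less favourable stated power. Items 2 and 3 are also text, though the sponsor should decide whether to accept the small shortfall in item 3. All of this should be settled before the interim, because event totals or bounds changed after unblinded data have been seen would be hard to defend.

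### The interim futility bound is printed as Z<0.41 and as p>0.6599, but these are not the same rule under any p-value convention

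*Protocol*

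**What the plan says.** Protocol Section 11.4 describes an "asymmetric two-sided non-binding two-stage group sequential design with 90% power and 2.5% type-1 error". At the interim, after at least 81 events:

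- Futility: "stage 1 will conclude futility if Z<0.41 (nominal p-value > 0.6599), favouring FMT".
- Superiority: "superiority if Z>2.75 (H0: Reject, nominal p<0.006) favouring FMT".
- Error spending is Hwang-Shih-DeCani with "Gamma = -4 (one-sided, stage one spent error =0.003".
- For the final look, "at the final analysis, the null hypothesis for efficacy will be rejected if p<0.047".

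Section 11.1 repeats only the timing and the efficacy level: "an interim analysis will be carried out after 81 events (alpha = 0.006". The futility p-value appears nowhere else in the protocol, and no passage says which tail it refers to.

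**The concern.** A bound given on two scales must select the same results on both. The superiority bound fixes the direction of Z: large positive values favour FMT. A futility bound just above zero should then correspond to a one-sided p for benefit of about one third, or a two-sided p of about two thirds that applies only on the FMT side. The printed figure lies near the two-sided value but does not equal it, and it carries no condition on direction.

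This is the pre-specified threshold for advising that a phase III trial stop. The Data Monitoring Committee sees unblinded efficacy data at the interim (Section 13), and the Trial Steering Committee advises the funder on applying the stopping rules (Section 12). If the report in front of them shows p-values, they could reach a different recommendation from a committee working from Z. Settling the reading once the data are known would be a choice made with knowledge of the result.

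**Working it through.** **Inputs.** From Section 11.4: futility Z<0.41 with p>0.6599; superiority Z>2.75 with p<0.006; one-sided type I error 0.025; spending parameter −4; 90% power; non-binding futility. From Section 11.1: 81 events at the interim, 1:1 allocation, design hazard ratio 0.625.

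**1. Convention used for the superiority p-value.** 2 × [1 − Φ(2.75)] = 2 × 0.00298 = 0.00596. The printed 0.006 is therefore two-sided, and the one-sided 0.00298 is the stage one spend of 0.003.

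**2. The same conversion for the futility bound.**

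- One-sided p for FMT benefit: 1 − Φ(0.41) = 0.3409.
- Two-sided p: 2 × 0.3409 = 0.6818.
- Lower tail: Φ(0.41) = 0.6591.

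Rounding of Z does not rescue either p-value. Over Z from 0.405 to 0.415, Φ(Z) runs from 0.657 to 0.661, so the one-sided p runs from 0.343 to 0.339 and the two-sided p from 0.685 to 0.678.

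**3. Where 0.6599 comes from.** Φ(0.4122) = 0.6599. To see whether 0.4122 is the unrounded bound, the design was rebuilt with two assumptions that the protocol does not state: an information fraction of 0.5, and Hwang-Shih-DeCani beta spending with parameter −2.

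- Stage one alpha: 0.025 × (1 − e²)/(1 − e⁴) = 0.00298, giving an upper bound of 2.750.
- Final two-sided level: 0.0476, beside the printed 0.047.
- Stage one beta: 0.10 × (1 − e)/(1 − e²) = 0.0269. With final drift 3.310, the lower bound is Φ⁻¹(0.0269) + 3.310 × √0.5 = 0.412, and its lower-tail probability is 0.6599.

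This reproduces both printed Z bounds and the figure 0.6599. It points to Z<0.41 as the intended rule, with its lower-tail probability mislabelled as a p-value. On that lower-tail scale the inequality would have to be Φ(Z) < 0.6599, the opposite of what is printed. Steps 1 and 2 do not depend on these assumptions.

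**4. What each reading means at 81 events.** The observed hazard ratio at a given Z is exp(−2Z/√81) = exp(−Z/4.5). When the true hazard ratio is HR, Z has mean −4.5 × ln(HR) and unit variance. That mean is 0 at HR 1, 2.115 at HR 0.625 and −1.514 at HR 1.4 (1.4 is an illustrative value for harm).

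| Reading of the rule | Z region | Observed HR | Stop if HR = 1 | Stop if HR = 0.625 |
|---|---|---|---|---|
| Z<0.41 as printed | Z < 0.41 | above 0.913 | 65.9% | 4.4% |
| p>0.6599, one-sided | Z < −0.412 | above 1.096 | 34.0% | 0.6% |
| p>0.6599, two-sided | −0.440 < Z < 0.440 | 0.907 to 1.103 | 34.0% | 4.2% |
| p>0.6599, lower tail | Z > 0.412 | below 0.913 | rule reversed | rule reversed |

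At a true hazard ratio of 1.4, the Z rule stops with probability Φ(0.41 + 1.514) = 97%. The two-sided reading stops with probability Φ(0.440 + 1.514) − Φ(−0.440 + 1.514) = 12%. Under that reading, Z = −1.5 would not meet the futility criterion.

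**The case against.** The strongest reply is that the operative rule can be recovered. Section 11.4 calls futility a lower-bound cut-off and prints Z first, with the p-value only in parentheses. A result of Z = −1.5 is below 0.41 on any reading of that lower bound. The bound is non-binding, the committee includes an independent statistician and works under its own charter, and the analysis plan is to carry the detail. The one-sided reading also sits badly with the words about favouring FMT, since a hazard ratio of 1.10 favours placebo. On the two-sided reading, which matches the superiority bound, the FMT-side cut-off hardly moves (Z 0.44 against 0.41), and the stopping probability at the design effect is 4.2% against 4.4%.

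Much of this stands. Type I error is not at risk, Z<0.41 is very probably what was meant, and a mechanical stop on the wrong scale is unlikely. If FMT works as assumed, the two-sided slip costs almost nothing. It does not make the printed figure right, however. With no effect, the two-sided reading halves the stopping probability just as the one-sided reading does, and it lets unfavourable results continue. The direction words after the futility bound add to that problem, because taken literally they confine futility to results leaning towards FMT. Nor is this an omission that the analysis plan can fill: a plan that copies the figure carries the error, and one that corrects it contradicts the protocol.

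**Conclusion.** The point holds: the futility threshold in Section 11.4 is wrong as written. No p-value convention makes p>0.6599 equivalent to Z<0.41. With no true effect, the futility stopping probability is 66% under the Z rule and 34% under either ordinary p-value reading. At the design hazard ratio of 0.625 the gap is 4.4% against 0.6% (one-sided) or 4.2% (two-sided). The largest practical difference on the two-sided reading is for results against FMT: 97% against 12% at an illustrative hazard ratio of 1.4.

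These probabilities assume a normal test statistic, 81 events and 1:1 allocation. The explanation of where 0.6599 came from is an inference that also needs an information fraction of 0.5 and a beta-spending parameter of −2. Against the 155 events in Section 11.1, 81 events would be 81/155 = 0.523. The mismatch itself needs neither assumption.

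**What to change.** State the futility rule in Section 11.4 on the Z scale only: futility if Z<0.41, with positive Z favouring FMT. If a p-value is wanted, give it as one-sided p>0.34 for FMT benefit. The two-sided equivalent is p>0.68 when the estimate favours FMT, or any estimate favouring placebo. Remove the direction words that follow the futility bound, and put the futility and superiority bounds on one stated scale.

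This costs one corrected line in the protocol, and a check that the analysis plan and the Data Monitoring Committee charter (neither available here) say the same. It should be done before unblinded interim data are seen. No redesign or change in sample size follows from it.

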11.5 Internal Pilot 'Go'/'No Go' progression

At the end of one year after the first site has opened for recruitment, we will assess the feasibility of the trial in an internal pilot. The criteria are shown below in the table in green.

| At the end of one year after the first site has opened to recruitment, we will assess the recruitment rate and the feasibility of continuing the PROMISE Trial. We will progress to the full trial by meeting the following 'go/'no go' criteria, as indicated by meeting the green criteria: *<80% will result in being flagged as amber and less than 64% red. | *Red | Amber | Green |
|---------------------------------------------------------------------------------------------------------------------------------------------------------------------------------------------------------------------------------------------------------------------------------------------------------------------------------------------------------------------------------------------|------|--------|------------|
| Open eight sites | <6 | 6 to 7 | 8 or more |
| Randomise 80 participants | <64 | 65-79 | 80 or more |
| Participant adherence (% of patients) | <64 | 65-79 | 80 or more |

11.6 Understanding the Mechanisms of Action

We will carry out a mediation analysis to assess the indirect and direct effects of potential mediators. We will perform mediation analysis to investigate whether the effect of FMT on reduced infection rate is explained by a third variable/s (mediator/s) that could be also under influence of FMT. The mechanistic endpoints will be fitted as mediators (for example: bacterial translocation, faecal/plasma biomarkers, microbial diversity etc.). Each potential mediating variable will be entered separately in mediation analyses to convey the indirect influence of FMT on the infection rate. If any of the potential mediators are not affected by the FMT, then it will not be considered as a mediator. A multi-level mediation analysis will be conducted with the estimation of various quantities for mediation including average causal mediation effect (indirect effect), average direct effect, and total effect. Subgroups will be investigated as moderating effects.

12 Trial Steering Committee (TSC)

An independent Trial Steering Committee (TSC) will be chaired by [name], an independent hepatologist who chaired the TSC of the safety and feasibility trial of FMT in cirrhosis (PROFIT Trial) which preceded this trial. The TSC will also include [name], an independent senior statistician, independent microbiologist, joint co-sponsor representative(s), the trial patient advocate, patient/lay representative(s) from the British Liver Trust and clinicians with experience relevant to the trial. The TSC will meet typically between six monthly and annually throughout the period of the trial, and at other times deemed necessary by the chief investigator, the sponsor or by the EME board.

The TSC will provide the overall supervision of the trial. The TSC will be responsible for monitoring trial progress and conduct and advising the NIHR EME over implementation of trial stopping rules on grounds of safety or efficacy. The TSC will approve the PROMISE-TSC terms of reference.

13 Data Monitoring Committee (DMC)

A Data Monitoring and Ethics Committee (DMC) will meet prior (or combined) with the TSC. The DMC will be chaired by [name], an independent hepatologist and include an independent microbiologist and an independent statistician. The DMC, in accordance with ICH GCP guidelines, is responsible for safeguarding the interests of trial participants, monitoring the main outcome measures including safety and efficacy (at interim), and monitoring the overall conduct of the trial. The DMC receives, on a periodical basis, unblinded data on trial recruitment, data quality and safety data. The DMC is required to assess emerging external evidence which might influence the ethical position of the trial. The committee is also expected to advise on any protocol modifications and whether the trial (or specific treatment groups) should be stopped early. The DMC will review recruitment and unblinded safety data per group allocated (and efficacy data at the interim analysis) and report to the TSC regarding any safety or ethical concern raised. The DMC will meet typically between six monthly and annually throughout the period of the trial, and at other times deemed necessary by the chief investigator, the sponsor or by the EME board.

The details of composition of the DMC and terms of reference will be set out in the Data Monitoring Committee charter, which the DMC will approve.

14 Trial Management Group (TMG)

The TMG will be responsible for the day-to-day management of the trial and will meet monthly to oversee the running of the trial. Chaired by the Chief Investigator, the membership will be composed of a chairperson, vice-chair, PROMISE Statisticians, PROMISE Trial Manager, PROMISE Trial Pharmacist and several of the PROMISE co-investigators. The TMG will be responsible for approval of the trial design, reviewing and advising on trial recruitment, reviewing the final results, approving publications and approval of secondary studies.

15 Direct Access to Source Data and Documents

The Investigator(s) will permit trial-related monitoring, audits, REC review, and regulatory inspections by providing the Sponsor(s), Regulators and REC direct access to source data and other documents (*e.g.*, participants' case sheets, blood test reports, X-ray reports, histology reports *etc.*).

16 Ethics & Regulatory Approvals

The trial will be conducted in compliance with the principles of the Declaration of Helsinki (1996), the principles of GCP and in accordance with all applicable regulatory requirements including but not limited to the Research Governance Framework and the Medicines for Human Use (Clinical Trial) Regulations 2004, as amended in 2006 and any subsequent amendments.

This protocol and related documents have been submitted and reviewed by the Health Research Authority (HRA), Research Ethics Committee (REC) [East of England Cambridge South], and to the Medicines and Healthcare products Regulatory Agency (MHRA) for Clinical Trial Authorisation.

Subsequent protocol amendments will be submitted to the REC and Regulatory Authorities for approval. An annual progress report (APR) will be submitted to the REC within 30 days of the anniversary date on which the favourable opinion was given, and annually until the trial is declared ended. Pharmacovigilance reporting (*i.e.*, DSUR) will be submitted to MHRA annually on the date of the first anniversary of the first CTA approval.

The Chief Investigator will submit a final report at conclusion of the trial to the KHP-CTO (on behalf of the Sponsor) and the REC within the timelines defined in the Regulations. The KHPCTO or delegate will upload the final report to EudraCT on behalf of the Sponsor.

17 Quality Assurance

This trial will be conducted according to the KHP-CTO Standard Operating Procedures as mandated by the KHP-CTO Quality Policy and Collaboration Agreement. Where appropriate, KCTU system SOPs will be followed.

18 Data Handling

The Chief Investigator will act as custodian for the trial data under the General Data Protection Regulations Act 2018 (GDPR Act 2018). The following guidelines will be strictly adhered to:

- All participant data will be pseudo-anonymised.
- All pseudo-anonymised data will be stored on a password-protected computer.
- All trial data will be stored in line with the Medicines for Human Use (Clinical Trials) Amended Regulations 2006 and the Data Protection Act 2018 and archived in line with the Medicines for Human Use (Clinical Trials) Amended Regulations 2006 as defined in the Kings Health Partners Clinical Trials Office Archiving SOP.

19 Data Management

A web based electronic data capture (EDC) system will be designed, using the InferMed Macro 4 system. The EDC will be created in collaboration with the trial analyst/s and the CI and maintained by the King's Clinical Trials Unit (KCTU) for the duration of the project. It will be hosted on a dedicated server within KCL.

The CI or delegate will request usernames and passwords from the KCTU. Database access will be strictly restricted through user-specific passwords to the authorised research team members. It is a legal requirement that passwords to the EDC are not shared, and that only those authorised to access the system are allowed to do so. If new staff members join the study, a user-specific username and password must be requested *via* the CI or delegate (*e.g.*, Trial Manager) from the KCTU team and a request for access to be revoked must be requested when staff members leave the project. Study site staff experiencing issues with system access or functionality should contact the CI or delegate (*e.g.*, Trial Manager) in the first instance.

Participant initials and date of birth will be entered on the EDC. NHS number, email addresses, participant names and addresses and full postcodes will not be entered into the EDC. No data will be entered onto the EDC system unless a participant has signed a consent form to participate in the trial. Source data will be entered by recruiting site staff, typically within 30

days of data collection by authorised staff onto the EDC by going to www.ctu.co.uk and clicking the link to access the MACRO 4 EDC system. A full audit trail of data entry and any subsequent changes to entered data will be automatically date and time-stamped, alongside information about the user making the entry/changes within the system.

The CI team will undertake appropriate reviews of the entered data where appropriate for the purpose of data cleaning and will request amendments as required. No data will be amended independently of the study site responsible for entering the data. Further details will be covered in a separate data management plan.

To ensure completeness of data, participants will be contacted *via* telephone if data is missing *e.g.*, questionnaires, blood results and all efforts will be made to ensure a full and complete record of data has been collected.

The investigator/centres will keep records of all participants (sufficient information to link records *e.g.*, Case Report Form (CRF), hospital records and samples), all original signed informed consent forms and copies of the CRF pages which will then be archived following the trial close out visit.

All data will be entered directly onto the CRF; the CRF would then be considered a source document. If the CRF is then transmitted to the sponsor, the trial site must retain a copy to ensure that the PI has an independent account from the sponsor as to what has occurred during the trial at his/her site.

At the end of the trial, the site PI will review all the data for each participant and provide electronic sign-off to verify that all the data is complete and correct. At this point, all data can be formally locked for analysis.

Upon request, the KCTU will provide a copy of the final exported dataset to the CI in .csv and Excel 2003 format and the CI will onward distribute as appropriate. Trial data will be entered into an electronic CRF database (InferMed MACRO) managed by the KCTU.

20 Publication Policy

The study findings will be disseminated by conventional academic routes, aiming for high impact open access peer-reviewed journal(s), and by involvement with patient support groups, wider media and NHS organisations to ensure a broad readership. In year 1 we will publish the trial protocol. At the end of the trial, the results will be published in one or more high impact open access journals and will include presentations at prominent gastroenterology and hepatology national and international conferences including British Association for the Study of the Liver (BASL), British Society of Gastroenterology (BSG), European Association for the Study of the Liver (EASL) and American Association for the Study of Liver Disease (AASLD) Annual Conferences. Authorship eligibility for publications will be based on the Chief Investigator's judgement on the individual's level of contribution in the design, conduct, and/or analysis of the trial.

We will ensure the research impacts on the management of patients with advanced cirrhosis and shapes policy and guideline development ensuring the data is included in relevant Cochrane reviews and that NICE, BSG and other bodies involved in the development of

national/international guidelines are aware when relevant. As a policy, written dissemination will be in a style that is understandable and useable for all stakeholders including NHS commissioners, clinicians, funding bodies, service users, patient support charities and the general public.

The British Liver Trust (BLT) will be central in leading the dissemination of the trial results and ensuring that the public and patients will be kept fully informed. They will also disseminate relevant findings through their website, newsletters and using social media platforms. At the end of the trial, we will hold a public webinar in conjunction with the BLT as an opportunity to disseminate the study findings and to bring everyone together to look at what was created and share learnings.

[name] is a scientific advisor to The House of Commons All-Party Parliamentary Group on Liver Health, and [name], Drs [name], [name], [name] and [name] sit on the Gut Microbiota for Health Expert Panel. We will continue to utilise the links of the Policy Institute at King's College London who have worked with [name] [name] (outgoing Chief Medical Officer) for many years (she is a Visiting Professor and the UK Special Envoy on antimicrobial resistance). We will issue joint press releases coordinated between KCL, King's Health Partners, the NIHR and the British Liver Trust. I will also make myself available for press interviews to discuss study findings with interested media parties. The paradigm shift and the impact that this type of research could have on changing the way that we treat patients with CLD is immense and far-reaching.

To potentially be able to reduce the susceptibility and incidence of infection in this group of individuals that will lead to less prescription of antibiotics, reduced hospitalisations and incidence of antimicrobial resistance would be of huge societal benefit and offer huge cost savings to the NHS. If FMT is shown to have clinical utility and improves outcomes in patients with cirrhosis, this could be integrated into clinical guidelines within the decade and particularly lead to a reduction in the use of prophylactic antibiotics where antimicrobial resistance rapidly develops.

21 Insurance / Indemnity

The Co-Sponsors insurance and indemnity schemes apply. Indemnity is provided by the Clinical Negligence Scheme for the Trust and insurance is provided by King's College London.

22 Financial Aspects

